3.5 Determination of Sample Size

The primary efficacy endpoint is the change from Baseline to Week 5 in the Hamilton Depression Scale (17 Items) (HAMD-17) total score. For Stage 1, Baseline is Study Week 0 and Week 5 is Study Week 5. For Stage 2, Baseline is Study Week 5 and Week 5 is Study Week 10.

A total sample size of 168 evaluable subjects is estimated to provide at least 80% power at a two-sided significance level of 0.05 assuming a mean change in the HAMD-17 total score of -7.8 (SD=8) and -10 (SD=8) in Stage 1, and -2.8 (SD=6) and -6.0 (SD=6) in Stage 2 for the placebo and pimavanserin groups, respectively.

For the above calculation, the weight for each double-blind treatment stage is equal to 0.5 and it is assumed that approximately 70% of placebo subjects will be non-responders at the end of Stage 1.

Adjusting for a potential non-evaluable rate of up to 10%, approximately 188 subjects will be randomized into Stage 1 (47 to pimavanserin and 141 to placebo). It is anticipated that approximately 98 subjects will be randomized into Stage 2 (49 to pimavanserin and 49 to placebo).

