4. ANALYSIS SETS

Randomized Analysis Sets

Randomized Analysis Set for Stage 1 – The Randomized Analysis Set for Stage 1 (RAS1) will consist of all subjects who were randomized into Stage 1.

Randomized Analysis Set for Stage 2 – The Randomized Analysis Set for Stage 2 (RAS2) will consist of all subjects who were placebo non-responders from Stage 1 and who were randomized into Stage 2.

Subjects will be classified according to the randomized treatment assignment.

Safety Analysis Sets

Safety Analysis Set for Stage 1 – The Safety Analysis Set for Stage 1 (SAS1) will consist of all subjects who were randomized into Stage 1 and received at least one dose of study drug in Stage 1.

Safety Analysis Set for Stage 2 – The Safety Analysis Set for Stage 2 (SAS2) will consist of all subjects who were placebo non-responders from Stage 1, were randomized into Stage 2, and received at least one dose of study drug in Stage 2.

Subjects will be classified according to the actual treatment received.

Full Analysis Sets

Full Analysis Set for Stage 1 – The Full Analysis Set for Stage 1 (FAS1) will consist of all subjects who were randomized into Stage 1, received at least one dose of study drug in Stage 1, and have both a Baseline (Study Week 0) value and at least one post-Baseline value for the HAMD-17 total score in Stage 1.

Full Analysis Set for Stage 2 – The Full Analysis Set for Stage 2 (FAS2) will consist of all subjects who were placebo non-responders from Stage 1, were randomized into Stage 2, received at least one dose of study drug in Stage 2, and have both a Baseline (Study Week 5) value and at least one post-Baseline value for the HAMD-17 total score in Stage 2.

Subjects will be classified according to the randomized treatment assignment.

Per-protocol Analysis Sets

Per-protocol Analysis Set for Stage 1 – The Per-protocol Analysis Set for Stage 1 (PAS1) will consist of a subset of subjects in FAS1 who do not have any protocol deviation which is considered to have substantial impact on the primary efficacy outcome. The precise reasons

Statistical Analysis Plan
2018

21 August

for excluding subjects from PAS1 will be fully defined and documented *a priori* before the clinical database lock.

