13.3 Other Secondary Efficacy Analyses

ANCOVA analyses for the secondary efficacy endpoints in this section will be performed using (1) the observed values (i.e., missing data will not be imputed) and (2) the last observation carried forward (LOCF) method for missing data (Note: for subjects without post-Baseline values, the Baseline values will be carried forward).

Remission rate at the end of the two 5-week treatment periods

Remission is defined as a HAMD-17 total score less than or equal to 7. Missing HAMD-17 total scores will be considered as non-remissions and the subjects with missing HAMD-17 total scores will be included in the denominator of the remission rate.

The remission rate will be compared between the pimavanserin and placebo groups within each stage using Pearson's chi-square test.

Let n be the total number of subjects in FAS1, n_{1q} be the number of placebo subjects in FAS1, n_{1p} be the number of pimavanserin subjects in FAS1, n_{2q} be the number of placebo subjects in FAS2 (i.e., placebo non-responders in Stage 1, were randomized to the placebo group in Stage 2, received at least one dose of study drug in Stage 2, and have both a Baseline [Study Week 5] value and at least one post-Baseline value for the HAMD-17 total score in Stage 2), and n_{2p} be the number of pimavanserin subjects in FAS2 (i.e., placebo non-responders in Stage 1, were randomized to the pimavanserin group in Stage 2, received at least one dose of study drug in Stage 2, and have both a Baseline [Study Week 5] value and at least one post-Baseline value for the HAMD-17 total score in Stage 2).

Let r_{1q} be the number of placebo remission subjects in FAS1 in Stage 1, r_{1p} be the number of pimavanserin remission subjects in FAS1 in Stage 1, r_{2q} be the number of placebo remission subjects in FAS2 in Stage 2, and r_{2p} be the number of pimavanserin remission subjects in FAS2 in Stage 2.

Let $q_1 = r_{1q} / n_{1q}$ and $p_1 = r_{1p} / n_{1p}$ be placebo and pimavanserin remission rate in Stage 1. Let $q_2 = r_{2q} / n_{2q}$ and $p_2 = r_{2p} / n_{2p}$ be placebo and pimavanserin remission rate in Stage 2, among

Statistical Analysis Plan
2018

21 August

placebo non-responders in Stage 1. Let w be the weight for Stage 1 and $1-w$ be the weight for Stage 2 (Note: w is 0.5 for this study).

The null hypothesis is: $w (P_1 - Q_1) + (1 - w) (P_2 - Q_2) = 0$.

The alternative hypothesis is: $w (P_1 - Q_1) + (1 - w) (P_2 - Q_2) \neq 0$.

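### Response and remission count a missing HAMD-17 as failure, but the FAS1/FAS2 denominators leave out subjects with no post-Baseline HAMD-17 in the stage, so unequal early loss can tilt these secondary comparisons (minor)

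*SAP*

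**What the plan says.** **Missing-data rule.** SAP 13.3 says of remission: "Missing HAMD-17 total scores will be considered as non-remissions and the subjects with missing HAMD-17 total scores will be included in the denominator". Response is analyzed by the same method with response in place of remission, so the rule reaches response by reference.

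**Denominators.** The same section begins "Let n be the total number of subjects in FAS1" and continues "n_{1q} be the number of placebo subjects in FAS1, n_{1p} be the number of pimavanserin subjects in FAS1". For Stage 2, "n_{2q} be the number of placebo subjects in FAS2", and pimavanserin is defined in the same way. These counts are the denominators of the rates and enter the variance in Equation (3).

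**Entry to those sets.** SAP 4 requires randomization and dosing in the stage. For FAS1 the subject must also "and have both a Baseline (Study Week 0) value and at least one post-Baseline value for the HAMD-17 total score in Stage 1"; for FAS2, "have both a Baseline (Study Week 5) value and at least one post-Baseline value for the HAMD-17 total score in Stage 2". SAP 13.3 repeats the FAS2 condition when it defines the Stage 2 counts.

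**Related text.** SAP 12 applies FAS1 and FAS2 to all efficacy analyses, and Protocol 9.3 assigns its full analysis set to all efficacy endpoints. SAP 4 also defines RAS1/RAS2 (all randomized) and SAS1/SAS2 (all dosed), but these endpoints do not use them. The dichotomized CGI-I in SAP 13.3 also treats a missing score as not improved, and is compared within FAS1 and FAS2.

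**The concern.** A missing-equals-failure endpoint can be scored for every randomized subject, so it does not need a post-Baseline rating. Requiring one limits the rule to subjects rated at least once in the stage who lack the end-of-stage score. Subjects with no rating at all, for whom most is missing, leave both numerator and denominator.

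That exclusion happens after randomization and may depend on treatment, for example through early adverse events. Protocol 1.1.2 reports nausea in 6.9% versus 4.3% and confusional state in 5.9% versus 2.6% on 34 mg versus placebo. Those figures come from Parkinson's disease psychosis and do not predict dropout here, but they make unequal early loss plausible. An arm that loses more subjects before any rating has its rate raised more. Counting missing as failure would otherwise guard against this.

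Nothing else in the SAP restores these subjects. The two sensitivity analyses in SAP 13.1.2 cover the HAMD-17 total score only and run on the per-protocol sets or the FAS. The carry-forward of Baseline in SAP 13.3 is stated for the ANCOVA analyses.

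**Working it through.** **1. The plan's own figures.** SAP 3.5 gives Stage 1 changes of -7.8 and -10 (SD 8), Stage 2 changes of -2.8 and -6.0 (SD 6), weight 0.5, 168 evaluable subjects (42 and 126 at 1:3) and 70% placebo non-responders (0.70 × 126 = 88, or 44 per arm).

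Z = (0.5 × 2.2 + 0.5 × 3.2) / √[0.25 × 64 × (1/42 + 1/126) + 0.25 × 36 × (1/44 + 1/44)] = 2.7 / √(0.508 + 0.409) = 2.82

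Power = Φ(2.82 - 1.96) = 80.5%, which agrees with the stated minimum of 80%. 168/0.9 = 187, against 188 stated (rounded up for 1:3), and 0.70 × 141 = 98.7, against 98. None of this depends on the present point. It supplies the arm sizes used below: 47 and 141 in Stage 1, 49 and 49 in Stage 2.

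**2. Effect of the denominator.** Let s be an arm's success rate when all randomized subjects count, and d the share with no rating (or no dose). The FAS rate is s/(1 - d). With equal d, both arms are inflated by the same factor (1/0.9 = 1.11 at d = 10%), and equal arms stay equal.

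**3. Unequal loss, no true difference.** Assumed: s = 30% in Stage 1 and 18% in Stage 2 in both arms, with the same loss in both stages. The spurious combined difference is 0.5 × [s1/(1 - dP) - s1/(1 - dQ)] + 0.5 × [s2/(1 - dP) - s2/(1 - dQ)], where P is pimavanserin and Q placebo.

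- 3% vs 1%: 0.5 × (0.3093 - 0.3030) + 0.5 × (0.1856 - 0.1818) = 0.5 points
- 5% vs 2%: 0.5 × (0.3158 - 0.3061) + 0.5 × (0.1895 - 0.1837) = 0.8 points
- 10% vs 3%: 0.5 × (0.3333 - 0.3093) + 0.5 × (0.2000 - 0.1856) = 1.9 points

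Error rates by simulation of Equation (3) with w = 0.5, 47/141 and 49/49:

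| Loss, pimavanserin vs placebo | Shift (points) | Upper tail, FAS | Upper tail, randomized | Two-sided, FAS | Two-sided, randomized |
|---|---|---|---|---|---|
| 3% vs 1% | +0.5 | 3.0% | 2.5% | 5.4% | 5.4% |
| 5% vs 2% | +0.8 | 3.4% | 2.5% | 5.5% | 5.4% |
| 10% vs 3% | +1.9 | 5.1% | 2.5% | 6.5% | 5.4% |

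The 5.4% is a property of the normal approximation at these sample sizes, not of the denominators. Swapping the losses to 3% vs 10% gives -1.9 points and, in the same simulation, two-sided error of about 6.9%. With 10% vs 3% in Stage 1 only, the shift is 0.5 × (0.3333 - 0.3093) = 1.2 points and the upper tail 4.0%. For remission at an assumed 15% and 8%, 10% vs 3% in both stages gives 0.9 points and an upper tail of 3.4%, against 2.1%.

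**4. When a difference exists.** Assumed FAS response of about 45% vs 30% in Stage 1 and 30% vs 15% in Stage 2, with 10% excluded from pimavanserin only (5 of 47 and 5 of 49).

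- FAS: 0.5 × (19/42 - 42/141) + 0.5 × (13/44 - 7/49) = 15.4 points, p = 0.011
- All randomized: 0.5 × (19/47 - 42/141) + 0.5 × (13/49 - 7/49) = 11.4 points, p = 0.045

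With 10% excluded from placebo only, the difference moves from 14.7 to 17.0 points (p 0.014 to 0.003). With 10% from every arm, it moves from 14.5 to 12.9 (p 0.019 to 0.024).

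**The case against.** **The FAS is a prespecified choice.** Protocol 9.3 and SAP 12 both name it, SAP 13.3 restates the FAS2 condition openly, and within the FAS the rule works as written. This stands: the text does not contradict itself. But Protocol 9.4.3 leaves the details of the binary analyses to the SAP, and the failure rule chosen there does not need the post-Baseline condition.

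**A reader might infer that every early dropout is lost.** The documents do not support that. HAMD-17 is scheduled at the Week 10/ET visit, Protocol 4.4 and 6.5.14 ask sites to make every effort to obtain that visit, and SAP 5.3.1 uses early-termination assessments. A subject who stops in the first week but is rated at that visit stays in FAS1 and counts as a failure if the Week 5 score is missing. Only never-rated and never-dosed subjects leave.

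**The loss rates are assumed.** SAP 3.5's "Adjusting for a potential non-evaluable rate of up to 10"% is a planning allowance and is not tied to loss before the first rating. Stage 2 entrants have already reached Week 5, so equally high loss there is doubtful. Both objections stand, which makes 10% vs 3% an upper illustration.

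**The bias is relative to an all-randomized null.** This is also true. If the target is the rate among subjects with a rating, the FAS rates answer it, but the SAP does not say that the rates are conditional in this way.

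**The exclusions will be visible.** SAP 6 lists subjects excluded from the FAS with reasons and tabulates set sizes by arm, so an imbalance could be seen and the rates recalculated, though not as a prespecified analysis.

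**Conclusion.** The point holds, at minor severity. The failure rule for response and remission covers only subjects with some post-Baseline HAMD-17 in the stage; those with none, and those never dosed, are removed. Equal loss leaves the test unbiased. Unequal loss shifts the combined difference by about 0.5 to 1.9 points in the scenarios shown, and two-sided error reaches about 6.5% against 5.4% when pimavanserin loses more. These figures rest on assumed response and loss rates, because the documents give neither.

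Two stronger readings are not supported. The rule does not systematically favour pimavanserin: it favours whichever arm loses more subjects before any rating, and the shift reverses when the losses are swapped. Nor does it touch the main conclusions: Protocol 9.4.10 tests the other secondary endpoints at a nominal 0.05 outside the hierarchy, and the primary and key secondary analyses do not use these denominators.

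**What to change.** In SAP 13.3, for response, remission and the dichotomized CGI-I, take as denominators all dosed subjects by randomized arm, or all of RAS1 and RAS2, and count a missing end-of-stage score as failure. If dosed subjects are chosen, use SAS1/SAS2 for membership only, because SAP 4 classifies those sets by treatment received. Apply the same denominators in the Pearson tests and, for response and remission, in Equation (3). CGI-I has only within-stage tests.

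Keep the FAS rates as a supportive table. At minimum, leave the FAS analysis in place and add the dosed or randomized version as a sensitivity analysis. Record the departure from Protocol 9.3 in SAP 19, which now reports no changes.

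The cost is SAP wording and one changed denominator per endpoint and stage, with no new data. Reported rates will be slightly lower, and under RAS the never-dosed subjects count as failures. If few subjects are excluded, the two tables will nearly agree.

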6.2.3 Clinical Global Impressions–Severity and Clinical Global Impressions-Improvement Scales

The CGI-S and CGI-I (Guy 1976) are scales used by the Investigator or designee to rate the severity of the disorder and the global improvement since beginning of the study. The CGI-S rates the severity of a patient's depression over the past 7 days. The CGI-I rates the change in a patient's depression over the past 7 days relative to the patient's symptoms at Baseline.

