9.6 Measures to Minimize Bias

9.6.1 Masking Procedures

This unmasked protocol version provides details of certain study design elements, procedures, and statistical methods that are not available in the masked version of the protocol.

This document is intended for use only by unmasked ACADIA or [REDACTED] personnel or their designated agents or for review only by IRBs, IECs, regulatory authorities, or any other entity considered suitable by ACADIA.

The information contained herein is UNMASKED and CONFIDENTIAL. Therefore, it must NOT be shared with or communicated to any individual at an investigational site or from site facing members of the clinical operations team of the CRO except with explicit and fully documented authorization from ACADIA.

Key elements revealed but that are masked in the masked protocol include:

- The 2-stage Sequential Parallel Comparison Design of the study and related details.
- The duration and timing of the efficacy period.
- Full definition of Stage 1 and Stage 2 baseline, admission and non-responder criteria and timepoints.
- Details of the statistical methodology that are specific to the Sequential Parallel Comparison Design

Investigators will receive the masked version of the clinical study protocol.

Investigators will be informed of the 10-week treatment period but will remain masked to the distinction between Stage 1 and Stage 2.

In order to maintain the masking of the re-randomization visit, Investigators will enter the HAMD-17 total score for the subject at every visit into Interactive Response Technology (IRT).

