5.2.2 Sheehan Disability Scale (SDS)

The SDS is a 3-item subject-facing questionnaire used to evaluate impairments in the domains of work, social life/leisure, and family life/home responsibility. Subjects rate each item using an 11-point scale ranging from 0 (not at all) to 10 (extremely). The mean score ranging from 0 to 10 will be calculated as the arithmetic mean of the scores for all 3 items and rounded to the nearest 2 decimal places. A higher mean score indicates greater disability. If a subject indicates that no work/school occurred, the mean score will be calculated as the arithmetic mean of the other two item responses (Social Life and Family Life/Home Responsibilities) and rounded to the nearest 2 decimal places. If either of the other two item responses is missing, or if the work/school response is missing and the subject does not indicate that no work/school occurred, the mean score will be missing.

The mean scores calculated based on only two item responses (Social Life and Family Life/Home Responsibilities) will be flagged in data listings. These results will be considered observed values for data summaries and analyses.

5.2.3 Clinical Global Impressions – Severity (CGI-S) and Clinical Global Impressions – Improvement (CGI-I) Scales

The CGI-S and CGI-I are scales used by the Investigator or designee to rate the severity of the disorder and the global improvement since beginning of the study. The CGI-S rates the severity of a subject's depression over the past 7 days and the CGI-S score ranges from 1 to 7:

- | | |
|-----------------------------|-------------------------------------------|
| 1 = Normal, not at all ill | 5 = Markedly ill |
| 2 = Borderline mentally ill | 6 = Severely ill |
| 3 = Mildly ill | 7 = Among the most extremely ill patients |
| 4 = Moderately ill | |

The CGI-I rates the change in a subject's depression over the past 7 days relative to the subject's symptoms at Baseline and the CGI-I score ranges from 1 to 7:

- | | |
|------------------------|---------------------|
| 1 = Very much improved | 5 = Minimally worse |
|------------------------|---------------------|

2 = Much improved

6 = Much worse

3 = Minimally improved

7 = Very much worse

4 = No change

Higher CGI-S and CGI-I scores denote more severe depression and less improvement in depression respectively. Missing CGI-S and CGI-I scores will not be imputed.

5.2.4 12-Item Short Form Health Survey (SF-12V2)

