5.3 Analysis Visit Windows

Baseline for Stage 1 of the study is defined as the last non-missing result, including results from repeated and unscheduled measurements, before first dosing in Stage 1. Baseline for subjects randomized into Stage 2 is defined as the results at Study Week 5.

Statistical Analysis Plan
2018

21 August

Efficacy, safety, and PK assessments will be summarized by analysis visit as presented in Table 2 below. For the Week 5 visit window only, the assessments collected on the date of randomization for the subjects who are randomized into Stage 2 will be selected for the analysis even if the Stage 2 randomization date is outside of the Study Day Interval, 33 - 39.

Table 2 Analysis Visit Windows

Analysis Visit	Study Visit	Target Study Day @	Study Day Interval
Baseline (Day 1 for Stage 1)	2 (Week 0)	1	≤ 1
Week 1	3 (Week 1)	8	2 – 11
Week 2	4 (Week 2)	15	12 – 18
Week 3	5 (Week 3)	22	19 – 25
Week 4	6 (Week 4)	29	26 – 32
Week 5	7 (Week 5)	36	33 – 39
Week 6	8 (Week 6)	43	40 – 46
Week 7	9 (Week 7)	50	47 – 53
Week 8	10 (Week 8)	57	54 – 60
Week 9	11 (Week 9)	64	61 – 67
Week 10	12 (Week 10)	71	68 – 78
Follow-up	~30-Day Follow-Up	101	≥79

@ Derivation of study day: study day = assessment date - first dose date + 1 if the assessment date ≥ first dose date, otherwise study day = assessment date – first dose date. Study day 1 is the day of first administration of study drug (pimavanserin or placebo).

Efficacy and safety assessments for Stages 1 and 2, when presented side by side or separately, will be summarized by analysis visit as presented in Table 3.

Table 3 Analysis Visit for Side-by-side or Separate Presentation of Stages 1 and 2

Data

Analysis Visit	Study Visit in Stage 1	Study Visit in Stage 2
Baseline (Day 1)	2 (Week 0)	7 (Week 5)
Week 1	3 (Week 1)	8 (Week 6)
Week 2	4 (Week 2)	9 (Week 7)
Week 3	5 (Week 3)	10 (Week 8)
Week 4	6 (Week 4)	11 (Week 9)
Week 5	7 (Week 5)	12 (Week 10)

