Inference will be made using the following weighted linear combination of stage-wise treatment effects:

$$Z = \frac{w(p_1 - q_1) + (1 - w)(p_2 - q_2)}{\sqrt{w^2 \text{Var}(p_1 - q_1) + (1 - w)^2 \text{Var}(p_2 - q_2)}} \sim N(0, 1),$$

$$\text{where, } \text{Var}(p_i - q_i) = \frac{p_i(1-p_i)}{n_{ip}} + \frac{q_i(1-q_i)}{n_{iq}}, \quad i = 1, 2. \quad (3)$$

Treatment response rate at the end of the two 5-week treatment periods

Treatment response is defined as a reduction from Baseline in HAMD-17 total score of 50% or more. The hypotheses and the analysis method for treatment response rate are the same as the hypotheses and the analysis method for the remission rate but with treatment response replacing remission.

Change from Baseline to Week 5 in CGI-S score

The change from Baseline to Week 5 in CGI-S score will be analyzed in a similar way as the primary analysis of the primary efficacy endpoint using the weighted linear combination test with the Baseline HAMD-17 total score replaced by the Baseline CGI-S score.

CGI-I score at Week 5

The CGI-I score will be analyzed in a similar way as the primary analysis of the primary efficacy endpoint using the weighted linear combination test. The differences are (1) the response is CGI-I score (as opposed to the change from Baseline in CGI-I score) and (2) the Baseline CGI-S score will be used as the covariate in the MMRM models.

The CGI-I data will also be dichotomized by combining “very much improved” and “much improved” into 1 category (“Improved”), and the remaining items into the other (“Not Improved”). For analysis purposes, missing CGI-I scores and CGI-I scores of 0 (“not assessed”) will be treated as “Not Improved”.

Statistical Analysis Plan
2018

21 August

The observed score and dichotomized data will be descriptively summarized by treatment group and visit. Treatment comparisons with respect to the dichotomized data within each stage for FAS1 and FAS2 will be performed using Pearson's chi-square test. No overall treatment comparisons combining Stages 1 and 2 will be made with respect to the dichotomized data.

Change from Baseline to Week 5 in SF-12 scores

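### Stage 2 CGI-I is rated against Study Week 0 but adjusted only for Study Week 5 CGI-S; adding Week 5 CGI-I would recover some precision, and no bias is at stake

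*SAP*

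**What the plan says.** Protocol 6.2.3 says that the two CGI scales "rate the severity of the disorder and the global improvement since beginning of the study". SAP 5.2.3 describes them in the same way and sets CGI-I against the subject's "symptoms at Baseline and the CGI-I score ranges from 1 to 7". Protocol 9.6.1 adds: "Investigators will be informed of the 10-week treatment period but will remain masked to the distinction between Stage 1 and Stage 2".

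For analysis, SAP 5.3 says: "Baseline for subjects randomized into Stage 2 is defined as the results at Study Week 5". SAP 12 repeats this for efficacy. SAP 13.3 analyses CGI-I by the method of the primary endpoint, with two differences: the response is the score itself rather than a change, and "the Baseline CGI-S score will be used as the covariate in the MMRM models". Protocol 9.4.3 names the same covariate.

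The schedule of assessments has no CGI-I at Study Week 0. It does have CGI-I at Study Week 5, and protocol 6.5.7 lists the scales at that visit ahead of re-randomization and dispensing.

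On missing values, SAP 5.2.3 says: "Missing CGI-S and CGI-I scores will not be imputed". FAS2 (SAP 4) asks that subjects "have both a Baseline (Study Week 5) value and at least one post-Baseline value for the HAMD-17 total score in Stage 2"; it sets no condition on either CGI score. For the dichotomized data, SAP 13.3 counts "missing CGI-I scores and CGI-I scores of 0" (not assessed) as not improved.

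**The concern.** Baseline means Study Week 0 to the rater and Study Week 5 to the Stage 2 model. A masked rater cannot re-anchor at Week 5, so a Stage 2 CGI-I score carries two parts: improvement over the five placebo weeks before re-randomization, and change during Stage 2. Only the second part can respond to the Stage 2 treatment.

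Week 5 CGI-S records how ill the subject is at that visit. It does not record how far the subject has moved since Week 0. Two subjects with the same Week 5 CGI-S can differ in CGI-I because they started at different severities, or because the rater's view of improvement differs. That variation remains in the Stage 2 residual.

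The other continuous secondary scales are each adjusted for their own baseline. CGI-I cannot be in Stage 1, where CGI-S is a sensible substitute. In Stage 2 a pre-treatment CGI-I exists and is not used. What is at stake is the width of the Stage 2 CGI-I interval and the power of the combined CGI-I test.

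**Working it through.** **1. The two reference points**

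| | Stage 1 | Stage 2 |
|---|---|---|
| CGI-I rated against | Study Week 0 | Study Week 0 |
| Analysis Baseline | Study Week 0 | Study Week 5 |
| CGI-S covariate taken at | Study Week 0 | Study Week 5 |
| Earlier CGI-I available | no | yes, Study Week 5 |

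**2. The plan's own figure.** The documents give no power for CGI-I. The HAMD-17 figure fixes the stage sizes: 168 evaluable at 1:3 gives 42 and 126, and 126 × 0.70 = 88.2, or 44.1 per Stage 2 arm.

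- Var1 = 64 × (1/42 + 1/126) = 2.032
- Var2 = 36 × (2/44.1) = 1.633
- Z = (0.5 × 2.2 + 0.5 × 3.2) / √(0.25 × 2.032 + 0.25 × 1.633) = 2.821
- Power = Φ(2.821 − 1.96) = 80.5%

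This agrees with the stated 80% or more.

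**3. Validity.** Both Stage 2 arms took placebo in Weeks 0 to 5 and were then randomized 1:1, so improvement by Week 5 is balanced in expectation. In simulation the estimated difference was the same without and with Week 5 CGI-I (for example −0.498 and −0.499). Null rejection was 5.1% and 5.0%.

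**4. Formula for the gain.** Let r be the partial correlation of Week 5 CGI-I with the outcome, given Week 5 CGI-S. Adding it multiplies the Stage 2 SE by √(1 − r²). With 42/126 and 44/44 subjects and equal residual SDs, the combined SE is proportional to √(0.03175 + 0.04545 × (1 − r²)).

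| r (assumed) | Stage 2 SE | Combined SE |
|---|---|---|
| 0.2 | −2.0% | −1.2% |
| 0.3 | −4.6% | −2.7% |
| 0.4 | −8.3% | −4.8% |
| 0.5 | −13.4% | −7.7% |

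**5. Two sets of assumptions for r.** Both use a single-visit ANCOVA in place of the MMRM.

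- *Set A*: 54 settings of a latent-severity model. SD of Week 0 severity was 0.2 to 0.7, of Stage 1 change 0.5 to 1.0, of Stage 2 change 0.7 to 1.1, and of rater error 0.3 or 0.6. The 88 least improved placebo subjects, by a noisy proxy, were re-randomized. The Stage 2 SE falls by 0.2 to 9.2% (median 2.0%), and the combined SE by 0.2 to 4.8% (median 1.4%).
- *Set B*: HAMD-17 simulated and the protocol's non-responder rule applied. CGI-I is tied to percentage improvement, in some settings with a subject-specific part that persists between visits. Partial r is about 0.32 to 0.53 and the Stage 2 SE ratio 0.946 to 0.849, a fall of 5 to 15%. By the formula in step 4, the combined SE falls by 3.1 to 8.6%. Adding Week 0 CGI-S instead lowers the Stage 2 SE by only 1.2 to 2.7%.

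**6. In power terms.** Suppose the planned combined CGI-I test had 80% power. A fall f in the combined SE gives Φ((1.96 + 0.8416)/(1 − f) − 1.96). For f = 1.4% this is 81.1%, and for 4.8% it is 83.7%. For the ends of set B, 3.1% and 8.6%, it is 82.4% and 86.5%.

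**7. Missing Week 5 CGI-I (set A, missing completely at random).** If missing values are filled with the FAS2 mean, the median fall in the Stage 2 SE is 1.9% with 5% missing and 1.7% with 10% missing. It is worse than planned in none of the 54 settings.

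**The case against.** The strongest reply is that nothing here is an error. The covariate is prespecified and is the same in protocol and SAP. The endpoint lies outside the testing hierarchy. Change in CGI-S from the Stage 2 Baseline already gives a clinician measure confined to Stage 2. And the size of the gain comes from assumptions alone. All of this stands, and it makes the point an improvement rather than a correction. It does not remove the case for using a pre-treatment measurement that the trial already collects.

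A reader might infer that an added covariate could do harm by losing subjects. If 4 of 88 are dropped from the enlarged model only, its SE exceeds the planned one in 31 of the 54 set A settings. That comparison is one-sided. The planned model also loses anyone without Week 5 CGI-S, which FAS2 does not require either; losing 4 of 88 costs it √(88/84) − 1 = 2.4%. When the same subjects are dropped from both models, the enlarged one is worse in none of the 54. The two scales share a visit and a rater role, and the documents give no missing rate. A fill rule is therefore a precaution.

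A reader might also infer that Stage 2 CGI-I tables will mislead about their reference point. This cannot be shown. SAP 1 places table specifications in a separate document, and both documents already state that CGI-I runs from the start of the study.

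**Conclusion.** The mismatch is in the text and holds as a matter of precision. Stage 2 CGI-I is anchored to Study Week 0, the model adjusts only for Week 5 CGI-S, and an available Week 5 CGI-I is left out.

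It would be tempting to conclude that the Stage 2 or combined CGI-I comparison is biased, or that it credits pimavanserin with placebo-period improvement. The documents do not support that: randomization at Week 5 balances that improvement between the arms.

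The gain is roughly 0 to 15% of the Stage 2 SE and 0 to 9% of the combined SE. Whether it is small is itself an assumption. It depends on how much CGI-I carries from visit to visit beyond what CGI-S records, and the documents give nothing on this. The direction and the absence of bias do not depend on the choice between the two sets of assumptions.

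**What to change.** Before database lock:

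- In the Stage 2 CGI-I MMRM only, add Study Week 5 CGI-I and its interaction with visit beside Week 5 CGI-S. Leave the Stage 1 model and the dichotomized within-stage tests as planned.
- Record the added covariate in SAP Section 19 as a change from protocol 9.4.3. That section now declares no changes.
- Treat a Week 5 CGI-I of 0 as missing.
- Fill a missing Week 5 CGI-I with the mean of FAS2 subjects who have a value, computed without regard to treatment, so that nobody is lost only because of the new covariate. State this as a covariate-only exception to SAP 5.2.3; outcome scores stay unimputed. It is not a change from protocol 9.4.3, since the protocol leaves missing-value handling to the SAP.

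The cost is one stage-specific model, one extra covariate with its interaction, and a declared departure from the protocol. No new data are needed and masking is unchanged. As a presentation suggestion only, Stage 2 CGI-I output could state that improvement is measured since Study Week 0.
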